9.4.1.1. Multiplicity Control

An overall type I error rate of 0.1 (2-sided) will be used.

The hypothesis testing will be conducted in a hierarchical manner with the test on the primary endpoint conducted first and the tests on major secondary endpoints conducted next. Within the major secondary endpoints, the gatekeeping approach in conjunction with graphical multiplicity control procedures will be applied. More details will be provided in the ISA SAP.

As the IA will not lead to an early ISA completion due to success, multiplicity adjustment is not required.

Nominal p-values will be calculated for all treatment comparisons.

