A target of 90 Bio-IR and Bio-NF participants will be randomized to receive JNJ 67864238 CCI [REDACTED] or placebo in a 3:2 ratio using permuted block randomization, stratified by baseline Crohn's Disease Activity Index (CDAI) score ( $\leq 300$ ,  $>300$ ) and biological refractory status (Bio-IR, Bio-NF). The treatment arms for this study will be as follows: JNJ-67864238 CCI [REDACTED] (N=54) and Placebo (N=36). Of note, the sample size has been chosen to assess a level of efficacy consistent with that observed with systemically available biological therapies for Crohn's disease.

An overview of this study design is presented in [Figure 1](#) below:

**Figure 1:** Schematic Overview of Study Design

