### 3. SAMPLE SIZE DETERMINATION

The sample size determination is based on the overall population, including both Bio-IR and Bio-NF participants. To examine the hypothesis that JNJ-active is superior to placebo as measured by CDAI, sample size is planned to achieve desirable operating characteristics of a predefined decision-making framework through simulation. A 90 Bio-IR or Bio-NF participants will provide about 90% power when the true treatment difference is 60 (placebo – JNJ-67864238) with standard deviation of 93 in the change in CDAI at Week 12 for both Bio-IR and Bio-NF populations.

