The Week 12 SES-CD Total score will be calculated only if the participant has a Week 12 endoscopy and at least one segment is evaluable. For segments evaluated and scored at baseline but not at Week 12, associated baseline segment scores will be carried forward to calculate the Total SES-CD score at Week 12. Otherwise, the Week 12 Total SES-CD will be missing.

Participants who meet 1 or more treatment failure rules (as specified for the primary endpoint) before Week 12 will be considered not to be in clinical remission, clinical response or clinical-biomarker response, either based on CDAI or PRO-2. For endoscopic response, the same treatment failure rules will be applied as appropriate. Any missing values at week 12 will be considered as no responder/remitter.

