#### 5.4.1.2. Estimands

The following describes the attributes of the estimands for the major secondary endpoints:

**Treatment by Week 12:** Same as Estimand 1, ie:

**Treatment:** CCI [REDACTED] for a 12 weeks period

- Experimental: JNJ-67864238 (PTG-200), CCI [REDACTED]
- Control: Matching Placebo tablets CCI [REDACTED]

**Population:** Participants with moderately to severely active Crohn's disease,

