#### Variables and Population-level Summary (for Estimands 5-10)

**Table 2: Variables and Population-level Summary for the estimand for each Major Secondary Endpoint**

Estimand	Variable (Endpoint)	Population-level summary
5	Change in the SES-CD from baseline (both main approach and alternative approach analyses will be performed )	Change from baseline in the SES-CD score at Week 12 or early withdrawal visit between experimental group and placebo.

6	Clinical response as measured by CDAI ( $\geq 100$ -point reduction from baseline in CDAI or CDAI $< 150$ )	Difference in percentage of subjects who achieved clinical response at Week 12 between experimental group and placebo.
7	Clinical remission rate as measured by CDAI (CDAI $< 150$ )	Difference in percentage of subjects who achieved clinical remission at Week 12 between experimental group and placebo.
8	PRO-2 remission defined as abdominal pain (AP) mean daily score (AP component of the CDAI) at or below 1 AND stool frequency (SF) mean daily score at or below 3, ie, AP $\leq 1$ and SF $\leq 3$	Difference in percentage of subjects who achieved PRO-2 remission at Week 12 between experimental group and placebo.
9*	Endoscopic response (defined as at least a 50% improvement from baseline in the SES-CD) (both main approach and alternative approach analyses will be performed )	Difference in percentage of subjects who achieved endoscopic response at Week 12 between experimental group and placebo.
10	Endoscopic remission (defined as an SES-CD score $\leq 2$ ) (both main approach and alternative approach analyses will be performed )	Difference in percentage of subjects who achieved endoscopic remission at Week 12 between experimental group and placebo.

\* For Endoscopic response, please refer to below prohibited medications for ICE category 2

- Immunomodulatory agents other than AZA, 6-MP, or MTX (including, but not limited to, 6-TG, cyclosporine, mycophenolate mofetil, tacrolimus, and sirolimus).
- Immunomodulatory biologic agents (including, but not limited to, TNF antagonists, natalizumab, ustekinumab, rituximab, vedolizumab). Ustekinumab is permitted in this study only in participants randomly assigned to ustekinumab and only as stipulated in this protocol.
- Experimental Crohn's disease medications (including, but not limited to, upadacitinib, filgotinib, ozanimod, etrolizumab, brazikumab, mirakizumab [formerly LY-3074828], risankizumab, GS-5745)
- Thalidomide or related agents.

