### Intercurrent Events and Corresponding Strategies:

The intercurrent events for all major secondary endpoints other than endoscopic response at Week 12 will be same as those used in the primary estimand, and are as follows:

1. A Crohn's disease-related surgery (with the exception of minor procedures such as drainage of a superficial abscess or seton placement, etc.);
2. A prohibited change in CD medication;
3. Discontinuation of study intervention due to lack of efficacy or an AE of worsening Crohn's disease;
4. Discontinuation of study intervention due to COVID-19 related reasons (like missing the assessment visit due to COVID-19 quarantine, but excluding COVID-19 infection)
5. Discontinuation of study intervention due to reasons other than lack of efficacy or an AE of worsening Crohn's disease (including AE/SAE due to COVID-19 infection).

ICEs will be handled by the same Estimands strategies as the primary Estimands strategies for the major secondary endpoints including clinical remission, clinical response, PRO-2 remission, endoscopic response (refer to Table 2 footnotes for ICE category 2), or endoscopic remission.

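### Endoscopic response has its own prohibited-medication list, so one Week 12 endoscopy can be scored a response under Estimand 9 and a treatment failure under the other SES-CD endpoints

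*SAP*

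**What the plan says.** SAP 5.3.1 applies the treatment failure rules to every efficacy endpoint unless otherwise specified. Five groups of medication change count: corticosteroids, oral 5-ASA, 6-MP/AZA/MTX, protocol-prohibited drugs started because of worsening Crohn's disease, and antibiotics. After failure, a continuous endpoint takes its baseline value and a binary endpoint is not achieved.

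Three places in SAP 5.4.1 then deal with endoscopic response:

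- SAP 5.4.1.1 says "For endoscopic response, the same treatment failure rules will be applied as appropriate".
- The Table 2 footnote, attached to Estimand 9 alone, lists its own drugs for intercurrent event category 2: immunomodulators other than AZA, 6-MP or MTX; biologics; experimental Crohn's drugs; and thalidomide or related agents. Within the biologics entry it adds "Ustekinumab is permitted in this study only in participants randomly assigned to ustekinumab and only as stipulated in this protocol".
- The intercurrent-event text in SAP 5.4.1.2 opens with "The intercurrent events for all major secondary endpoints other than endoscopic response at Week 12", says these match the primary estimand, and for endoscopic response refers back to the Table 2 footnote.

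SES-CD change (Estimand 5) and endoscopic remission (Estimand 10) carry no such footnote. SAP 5.4.2 lists a supportive endpoint of SES-CD reduction at several thresholds, including 50%, and handles intercurrent events as for the primary estimand.

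Protocol 6.5.1 lets participants who start or increase 5-ASA, immunomodulators, corticosteroids or antibiotics for Crohn's disease stay on study intervention, and classes them as treatment failures.

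**The concern.** Four endpoints are derived from one Week 12 endoscopy: SES-CD change, endoscopic response, endoscopic remission and the supportive 50% reduction. Three use the full set of failure rules and one does not. Nothing in the SAP explains why. A rationale based on endoscopy being centrally read or objective would apply equally to Estimands 5 and 10.

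Two consequences follow. First, the SAP can report two different Week 12 rates for the same 50% threshold, one as a major secondary endpoint and one as supportive. Second, someone whom Protocol 6.5.1 classes as a treatment failure can count as a success on a major secondary endpoint that SAP 5.3.5 places in the hierarchical testing scheme. A programmer working from SAP 5.4.1.1 and one working from Table 2 could produce different results, and both could claim to follow the plan.

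**Working it through.** **The plan's own figure.** The documents give no rate or power for endoscopic response. The only related figure is for the primary endpoint: 90 participants "will provide about 90% power when the true treatment difference is 60", "with standard deviation of 93 in the change in CDAI at Week 12". Protocol 9.4.1.1 sets alpha: "An overall type I error rate of 0.1 (2-sided) will be used". Allocation is "or placebo in a 3:2 ratio using permuted block randomization", that is 54 and 36.

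- Standard error = 93 × √(1/36 + 1/54) = 93 × 0.2152 = 20.01.
- 60 / 20.01 = 2.998, and 2.998 − 1.645 = 1.353.
- Power = Φ(1.353) = 0.912 by the normal approximation, or 0.908 by noncentral t. The stated figure is reproduced. It concerns CDAI, so nothing below alters it.

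**The two lists side by side.** Category 2 is read here as the SAP 5.3.1 medication rules, because the primary estimand is defined by meeting the treatment failure criteria.

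| Medication change | SAP 5.3.1 | Table 2 footnote |
|---|---|---|
| Corticosteroids | Failure | Not listed |
| Oral 5-ASA | Failure | Not listed |
| 6-MP/AZA, MTX | Failure | Expressly left out |
| Other immunomodulators, biologics, experimental drugs | Failure if started for worsening disease | Failure, no reason required |
| Antibiotics for Crohn's disease | Failure | Not listed |

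The footnote is narrower in four classes and wider in one respect.

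**One participant scored under each rule (assumed values).** SES-CD is 12 at baseline. An oral corticosteroid is started for worsening disease, the participant stays on study, and SES-CD is 6 at Week 12. The observed fall is (12 − 6)/12 = 50%.

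| Endpoint | Result |
|---|---|
| Estimand 5, SES-CD change | 12 − 12 = 0 (baseline assigned) |
| Supportive 50% reduction, SAP 5.4.2 | Not achieved |
| Estimand 9 under SAP 5.3.1 | Non-responder |
| Estimand 9 under the Table 2 footnote | Responder |

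If the Week 12 score were 2 instead, the fall would be 10/12 = 83%. The participant would be a non-remitter by rule in Estimand 10 and a responder in Estimand 9.

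The discrepancy needs all of the following: a medication change that fails under SAP 5.3.1 but is off the footnote list; no Crohn's-related surgery; no discontinuation for lack of efficacy or worsening disease; a scored Week 12 endoscopy; and an observed fall of at least 50%.

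**Size per participant, at planned arm sizes.** 1/54 = 1.9 percentage points (active); 1/36 = 2.8 points (placebo).

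**Direction.** The documents give no rescue rates. For illustration only, assume off-list changes in 5–15% of active and 5–25% of placebo participants, with a common 10–50% of these showing a halved score. The shift in the treatment difference is (active rate − placebo rate) × share halved. The extremes are (0.05 − 0.25) × 0.5 = −10 points and (0.15 − 0.05) × 0.5 = +5 points. The sign is not determined.

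**The case against.** The best defence is that the exception is deliberate. SAP 5.3.1 allows exceptions, the asterisk sits on Estimand 9 only, and the intercurrent-event text excepts endoscopic response openly and points to the footnote. SAP 5.4.1.1 qualifies its statement with *as appropriate*. Read together, a specific list qualifies a general default, and different estimands may legitimately handle the same event differently. Protocol 6.5.2 is also softer than 6.5.1, saying only that such participants may be considered failures. The Master protocol section on secondary endpoints is not among the documents.

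Much of this stands, and it rules out several stronger readings:

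- A reader might infer a flat contradiction in the SAP. The qualifier and the open exception do not support that. The fault is that the passages are not reconciled and the qualifier is undefined.
- A reader might infer that the list was copied from a trial with a ustekinumab arm. The documents do not show its origin. The protocol synopsis allows platform cohorts to have an active comparator, so general platform wording is equally possible. What is certain is that this cohort's only comparator is "Control: Matching Placebo tablets".
- A reader might infer that someone with no endoscopic improvement counts as a responder. The zero in Estimand 5 is an assigned value; the observed score must have fallen by at least half.
- A reader might infer bias in favour of the drug. The direction is unknown.

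The defence does not supply a reason for treating Estimand 9 differently from Estimands 5 and 10, nor for two rules at the same 50% threshold. SAP Appendix 2, which records changes to protocol-planned analyses, mentions only COVID-19 handling.

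**Conclusion.** The point holds as an unreconciled and unexplained difference in failure rules between endpoints taken from one endoscopy. It can change the reported endoscopic response rate by 1.9 points (active) or 2.8 points (placebo) per reclassified participant, assuming the planned arm sizes of 54 and 36. Neither the number of such participants nor the net effect on the treatment difference can be derived from the documents.

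The consequence is limited. Endoscopic response is not in the success or futility criteria of Protocol 9.2.2 or SAP Attachment 1, which use CDAI change and SES-CD change. Under SAP 5.3.5 it is tested only after a significant primary result. This is a minor correction, but it affects a result and is more than missing detail.

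**What to change.** Make these SAP changes before unblinding:

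1. Delete the Table 2 footnote and its asterisk, so that the medication rules of SAP 5.3.1 define category 2 for all SES-CD endpoints.
2. In the intercurrent-event text of SAP 5.4.1.2, remove both the exception for endoscopic response and the reference to the footnote. Deleting the footnote alone would leave that text pointing at nothing, and endoscopic response without a defined category 2.
3. In SAP 5.4.1.1, delete *as appropriate* from the sentence on endoscopic response.
4. Keep the narrower list, without the sentence on a ustekinumab arm, as a named sensitivity analysis for endoscopic response.

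The cost is SAP wording and one additional sensitivity output. No data collection, sample size or primary analysis changes. This concerns analysis rules only and proposes no change to permitted treatment.

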### Intercurrent Events and Corresponding Strategies:

The intercurrent events for all major secondary endpoints other than endoscopic response at Week 12 will be same as those used in the primary estimand, and are as follows:

1. A Crohn's disease-related surgery (with the exception of minor procedures such as drainage of a superficial abscess or seton placement, etc.);
2. A prohibited change in CD medication;
3. Discontinuation of study intervention due to lack of efficacy or an AE of worsening Crohn's disease;
4. Discontinuation of study intervention due to COVID-19 related reasons (like missing the assessment visit due to COVID-19 quarantine, but excluding COVID-19 infection)
5. Discontinuation of study intervention due to reasons other than lack of efficacy or an AE of worsening Crohn's disease (including AE/SAE due to COVID-19 infection).

ICEs will be handled by the same Estimands strategies as the primary Estimands strategies for the major secondary endpoints including clinical remission, clinical response, PRO-2 remission, endoscopic response (refer to Table 2 footnotes for ICE category 2), or endoscopic remission.

#### **5.4.1.3. Analysis Methods for the Estimands for the Major Secondary Endpoints**

The major secondary endpoints of clinical remission (either based on CDAI, SES-CD, or PRO-2), clinical response, endoscopic response, and clinical-biomarker response at Week 12 will be compared between PTG-200 group and the placebo group.

A logistic regression model will be used in the responder analyses with the treatment arm and population status (Bio-IR or Bio-NF), if applicable, as fixed factors, at 2-sided significance level of 0.1. In this model, baseline measurements may be included as covariates as appropriate. The change from baseline in the SES-CD score at Week 12 will be evaluated using MMRM model in comparing treatment difference by LS Mean (SD), LS mean (90% CI). P-Value was based on comparison with placebo model. And other statistical analysis as appropriate.

#### **5.4.2. Supportive Endpoint(s)**

Other endpoints to be evaluated across all post-baseline visits as appropriate:

- Change in AP from baseline based on a 0 to 10 numerical rating scale (NRS)
- Change in number of daily loose or watery stools
- Changes from baseline in the CDAI, PRO-2 (the sum of AP and SF subscores of the CDAI score), PRO-3 (the sum of AP, stool frequency, and general well-being subscores of the CDAI score), C-reactive protein (CRP), and fecal calprotectin
- Clinical remission (CDAI <150), PRO-2 remission (AP  $\leq$ 1 and SF  $\leq$ 3), and clinical response based on CDAI
- Endoscopic improvement based on a reduction from baseline in the SES-CD score ( $\geq$ 3 points, 25%, 50%), (both main approach and alternative approach analyses will be performed)
- Endoscopic healing (defined as the absence of mucosal ulcerations), (both main approach and alternative approach analyses will be performed)
- Patient's Global Assessment of Crohn's Disease Activity
- Change from baseline in multivariate score of biomarkers measured in mucosal biopsy samples, whole blood, serum, and/or stool
- Change in PROs as measured by the PROMIS-29 score

ICEs will be handled by the same Estimands strategies as the primary Estimands strategies for the supportive secondary endpoints. Participants who do not return for evaluation or have missing AP or SF scores at Week 12 will be considered not to be in PRO-2 remission (ie, clinical remission measured by AP and SF). Participants who do not return for evaluations or have missing CRP or fecal calprotectin values at Week 12 will be considered not to be in clinical-biomarker response unless the non-missing values at Week 12 already confirm a clinical-biomarker response. Any missing values at week 12 will be considered as no responder/remitter.

#### **5.4.2.1. Analysis Methods**

Descriptive statistics (i.e., mean, median, SD, IQ range, minimum, and maximum) will be used to summarize continuous variables. Counts and percentages will be used to summarize categorical variables. Graphical data displays (e.g., line plots) may also be used to summarize the data. The statistical model specified in the major secondary section will be applied for the other efficacy endpoints as appropriate.

#### **5.5. Tertiary/Exploratory Endpoint(s) Analysis**

Exploratory analysis will be performed to understand the potential factors of regional and/or subpopulation variability such as covariate-adjusted analyses, subgroup summaries if it is necessary.

#### **5.6. Safety Analyses**

Safety summaries will be based on the safety analysis set and participants will be analyzed based on the treatment the participants received.

For all continuous safety variables, descriptive statistics by intervention group will include the N, mean, standard deviation, median, minimum, and maximum. Categorical variables will be summarized by intervention group using frequency counts and percentages.

Safety analyses will be based on observed data (i.e., no data imputation).

##### **5.6.1. Extent of Exposure**

The number and percentage of participants who receive study intervention will be summarized by intervention group.

Study intervention duration is defined as (date of last dose of study intervention – date of first dose of study intervention) +1. Descriptive statistics for duration of study intervention (N, mean, SD, median, and range (minimum, maximum)) will be summarized by intervention group.

Total dose days of intervention is defined as the total number of days that study intervention was administered to the participant (excluding days off study intervention).

The number (%) of participants with a dose adjustment will be summarized by intervention group. Reasons for dose adjustments will also be summarized intervention group.

Descriptive statistics will be presented for the following parameters:

- Number of administrations
- Cumulative total dose
- Mean daily dose

The mean daily dose of study intervention is calculated as (sum of total daily dose during the intervention phase)/total dose days of intervention.

## 5.6.2. Adverse Events

The verbatim terms used in the CRF by investigators to identify adverse events will be coded using the Medical Dictionary for Regulatory Activities (MedDRA). Any AE occurring at or after the initial administration of study intervention through the day of last dose plus 30 days is considered to be treatment emergent. If the event occurs on the day of the initial administration of study intervention, and either event time or time of administration are missing, then the event will be assumed to be treatment emergent. If the event date is recorded as partial or completely missing, then the event will be considered to be treatment emergent unless it is known to be prior to the first administration of study intervention based on partial onset date or resolution date. All reported treatment-emergent adverse events will be included in the analysis. For each adverse event, the number and percentage of participants who experience at least 1 occurrence of the given event will be summarized by intervention group.

Summary tables will be provided for treatment-emergent adverse events:

- AEs
- Serious adverse events (SAEs)
- AEs leading to discontinuation of study agent
- Reasonably related AEs.
- Infections, including infections requiring with an oral or parenteral antibiotic treatment.
- Serious infections.

An infection is defined as any AE that was characterized by the investigator as an infection on the eCRF.

In addition to the summary tables, listings will be provided for participants who:

- Had SAEs
- Had AEs leading to discontinuation of study intervention/termination of study participation

A listing of participants who died will be provided.

Incidence of other treatment-emergent adverse events of [clinical, special] interest will be summarized as necessary.

## 5.6.3. Additional Safety Assessments

### 5.6.3.1. Clinical Laboratory Tests

Clinical laboratory tests will be displayed for the participants included in the safety analysis set. Clinical laboratory values are to be graded using National Cancer Institute Common Terminology Criteria for Adverse Events (NCI-CTCAE) version 5.0 (see [Table 3](#)). Descriptive statistics and graphical displays will be presented for chemistry and hematology at scheduled time points.

Change/percent change from baseline to time point will be summarized for chemistry, hematology, tests and displayed by intervention group.

- Summary of the observed values and changes from baseline over time through the final efficacy & safety visit for clinical laboratory parameters.
- Summary of maximum NCI-CTCAE toxicity grade for postbaseline laboratory values through Week 12 and through the final efficacy & safety visit for clinical laboratory parameters listed in [Table](#) . For toxicity grades, treatment emergent (TE) will be concluded if the postbaseline value is worse than the baseline value.
- Shift tables for selected clinical laboratory parameters (ALT, AST, alkaline phosphatase and total bilirubin) at Week 12.
- For abnormalities based on normal range and/or criteria: If the postbaseline value is above the upper limit and the baseline value is below the upper limit (eg, Normal or Low), then the postbaseline abnormality will be considered TE. The same applies to the postbaseline value being below the lower limit with the baseline value being above the lower limit (eg, Normal or High).
- If the baseline value is missing, a postbaseline abnormality will always be considered as TE.

Listings of participants with any abnormal postbaseline laboratory values of CTCAE grade  $\geq 2$  will also be provided.

The laboratory data to be summarized are as follows:

- **Hematology assessments:** hematocrit, hemoglobin, platelet count, total leukocytes and differential WBC count (neutrophils, lymphocytes, monocytes, eosinophils, and basophils)
- **Blood chemistry assessments:** ALT, AST, alkaline phosphatase, albumin, total and direct bilirubin, blood urea nitrogen, calcium, chloride, creatinine, phosphate, potassium, total protein, and sodium.

The baseline value for a participant is the value closest to but prior to the first dose of study agent (Week 0). Change from baseline is defined to be the assessment at the postbaseline visit minus the assessment at baseline. Summaries of laboratory data will be completed using all the available laboratory data at the time point of interest without imputing missing data. Shift tables summarize the number of participants with low, normal, and high values (determined by the laboratory normal ranges) at the post baseline visit for each of the classifications of low, normal, and high at baseline.

Table 3: Grading Criteria for Clinical Laboratory Tests [CTCAE Version 5.0]

Table 3: Grading Criteria for Clinical Laboratory Tests [CTCAE Version 5.0]					
Hematology Tests		Criteria			
Test	Direction	1	2	3	4
Hemoglobin (g/dL)	Increase	>0 - 2	>2 - 4	>4	
Hemoglobin (g/dL)	Decrease	<LLN - 10.0	<10.0 - 8.0	<8.0	
Lymphocytes (/mm  )	Increase		>4000 - 20,000	>20,000	
Lymphocytes (/mm  )	Decrease	<LLN - 800	<800 - 500	<500 - 200	<200
Neutrophils (/mm  )	Decrease	<LLN - 1500	<1500 - 1000	<1000 - 500	<500
Platelets (/mm  )	Decrease	<LLN - 75,000	<75,000 - 50,000	<50,000 - 25,000	<25,000
Total WBC count (/mm  )	Increase			>100,000	
Total WBC count (/mm  )	Decrease	<LLN - 3000	<3000 - 2000	<2000 - 1000	<1000
Chemistry Tests		Criteria			
Test	Direction	1	2	3	4
ALT	Increase	>ULN - 3.0 x ULN if baseline was normal; 1.5 - 3.0 x baseline if baseline was abnormal	>3.0 - 5.0 x ULN if baseline was normal; >3.0 - 5.0 x baseline if baseline was abnormal	>5.0 - 20.0 x ULN if baseline was normal; >5.0 - 20.0 x baseline if baseline was abnormal	>20.0 x ULN if baseline was normal; >20.0 x baseline if baseline was abnormal
AST	Increase	>ULN - 3.0 x ULN if baseline was normal; 1.5 - 3.0 x baseline if baseline was abnormal	>3.0 - 5.0 x ULN if baseline was normal; >3.0 - 5.0 x baseline if baseline was abnormal	>5.0 - 20.0 x ULN if baseline was normal; >5.0 - 20.0 x baseline if baseline was abnormal	>20.0 x ULN if baseline was normal; >20.0 x baseline if baseline was abnormal
Albumin (g/L)	Decrease	≥30 - <LLN	≥20 - <30	<20	
Alkaline Phosphatase	Increase	>ULN - 2.5 x ULN if baseline was normal; 2.0 - 2.5 x baseline if baseline was abnormal	>2.5 - 5.0 x ULN if baseline was normal; >2.5 - 5.0 x baseline if baseline was abnormal	>5.0 - 20.0 x ULN if baseline was normal; >5.0 - 20.0 x baseline if baseline was abnormal	>20.0 x ULN if baseline was normal; >20.0 x baseline if baseline was abnormal
Bilirubin (total)	Increase	>ULN - 1.5 x ULN if baseline was normal; > 1.0 - 1.5 x baseline if baseline was abnormal	>1.5 - 3.0 x ULN if baseline was normal; >1.5 - 3.0 x baseline if baseline was abnormal	>3.0 - 10.0 x ULN if baseline was normal; >3.0 - 10.0 x baseline if baseline was abnormal	>10.0 x ULN if baseline was normal; >10.0 x baseline if baseline was abnormal
Corrected Calcium* (mmol/L)	Increase	>ULN - ≤2.9	>2.9 - ≤3.1	>3.1 - ≤3.4	>3.4

Corrected Calcium (mmol/L)	Decrease	$\geq 2.0 - < \text{LLN}$	$< 2.0 - \geq 1.75$	$< 1.75 - \geq 1.5$	$< 1.5$
Creatinine	Increase	$> \text{ULN} - \leq 1.5 \times \text{ULN}$	$> 1.5 - 3.0 \times \text{baseline}; > 1.5 - 3.0 \times \text{ULN}$	$> 3.0 \times \text{baseline}; > 3.0 - 6.0 \times \text{ULN}$	$> 6.0 \times \text{ULN}$
Glucose (mmol/L)	Decrease	$< \text{LLN} - 3.0$	$< 3.0 - 2.2$	$< 2.2 - 1.7$	$< 1.7$
Potassium (mmol/L)	Increase	$> \text{ULN} - \leq 5.5$	$> 5.5 - 6.0$	$> 6.0 - 7.0$	$> 7.0$
Potassium (mmol/L)	Decrease	$< \text{LLN} - 3.0$		$< 3.0 - 2.5$	$< 2.5$
Sodium (mmol/L)	Increase	$> \text{ULN} - 150$	$> 150 - 155$	$> 155 - 160$	$> 160$
Sodium (mmol/L)	Decrease	$< \text{LLN} - 130$	$129 - 125$	$124 - 120$	$< 120$

